	
The Investigator should withdraw a patient from all study-related treatment for any of the following reasons:
 

• An unacceptable adverse event or safety observation, such as a persistent moderate toxicity that is intolerable to the patient, that is in the opinion of the Investigator clearly attributed to TTI-621

• An unacceptable adverse event or safety observation, such as a persistent moderate toxicity that is intolerable to the patient, that is in the opinion of the Investigator clearly attributed to doxorubicin and the patient has received fewer than four cycles of doxorubicin. A patient who has completed four cycles of doxorubicin treatment and experiences an adverse event that requires discontinuation of doxorubicin treatment despite optimal prophylaxis and supportive care and is receiving clinical benefit may be eligible to continue to TTI-621 monotherapy with the next cycle (Cycle 5 or Cycle 6) after discussion with the Sponsor Medical Monitor and provided the patient has not experienced disease progression and TTI-621 re-treatment guidelines as described in Section 9.2.2 are met; the patient may be replaced or an additional patient may be enrolled for the purposes of having a heterogeneous population for evaluation of safety and clinical activity as described in Section 6.7.

• Any event which would cause TTI-621 or doxorubicin to be modified by more than two dose reductions or to be held for more than 42 days from the last administered dose and is not attributable to a particular agent of the combination regimen; exception is made for patients who are receiving meaningful clinical benefit and the investigator feels, with Sponsor Medical Monitor concurrence, that continued treatment is in the best interest of the patient

• Any treatment-related adverse event that is deemed life-threatening, regardless of grade; exception is made for patients in whom the life-threatening adverse event is attributed to doxorubicin and has occurred despite optimal prophylaxis and medical support and the patient is receiving clinical benefit and has received at least four cycles of doxorubicin treatment and the investigator feels, with Sponsor Medical Monitor concurrence, that continuation with TTI-621 monotherapy would be reasonable; the patient may be replaced or an additional patient enrolled for the purposes of having a heterogeneous population for evaluation of safety and clinical activity as described in Section 6.7.

• Documentation of objective (radiographic) disease progression; for patients with asymptomatic progression and in the absence of unacceptable toxicity, the patient should continue treatment and a confirmation scan should be

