### 5.2.2. Doxorubicin

Doxorubicin will be administered with prophylaxis as described in [Section 5.2.1.1](#). In Cycle 1 through Cycle 6, doxorubicin will be used in accordance with standard of care with intravenous infusion at a dose of 75 mg/m^2 on Day 1 of each 21-day cycle for a maximum of six cycles (18 weeks). It is intended that each patient will receive six cycles of doxorubicin as fewer than six cycles provides less benefit to the patient compared to six or more cycles and guidelines for prophylaxis for prevention of doxorubicin-mediated dose-limiting neutropenia are provided in [Section 5.2.1](#). Investigators should consult the approved doxorubicin hydrochloride package insert for complete prescribing information (including warnings, precautions, contra-indications, adverse reactions and dose modifications) and may follow institutional procedures for the administration of doxorubicin. Doxorubicin should be made up to a volume of 100 mL and administered through a free-flowing catheter at 75 mg/m^2 by intravenous infusion in less than 60 minutes. The rate of infusion should be decreased if erythematous streaking along the vein proximal to the site of infusion or facial flushing occur.

In any cycle in which doxorubicin and TTI-621 are administered on the same day, doxorubicin treatment will precede administration of TTI-621. A delay before initiation of TTI-621 is not mandated.

As described below in [Section 5.2.3](#), it is intended that after completion of the planned six cycles of doxorubicin treatment, patients will transition to TTI-621 monotherapy and continue on monotherapy until progression. Patients who are unable to complete the planned six cycles of doxorubicin treatment

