- An unacceptable adverse event or safety observation, such as a persistent moderate toxicity that is intolerable to the patient, that is in the opinion of the Investigator clearly attributed to doxorubicin and the patient has received fewer than four cycles of doxorubicin. A patient who has completed four cycles of doxorubicin treatment and experiences an adverse event that requires discontinuation of doxorubicin treatment despite optimal prophylaxis and medical support and who is receiving clinical benefit may be eligible to continue on study receiving TTI-621 monotherapy after discussion with the Sponsor Medical Monitor but may be replaced or an additional patient may be enrolled for the purposes of evaluating safety and activity of the combination of doxorubicin and TTI-621 as described in [Section 6.7](#).
- Unacceptable toxicity which in the opinion of the Investigator cannot be attributed to a specific study agent
- Any event which would cause TTI-621 or doxorubicin to be modified by more than two dose reductions or to be held for more than 21 days from the last administered dose and is not attributable to a particular agent of the combination regimen; exception is made for patients who are receiving meaningful clinical benefit and the investigator feels, with Sponsor Medical Monitor concurrence, that continued treatment is in the best interest of the patient
- Any treatment-related adverse event that is deemed life-threatening, regardless of grade; exception is made for patients in whom the life-threatening adverse event is attributed to doxorubicin despite optimal prophylaxis and medical support and the patient is receiving clinical benefit and the patient has received at least four cycles of doxorubicin treatment and the investigator feels, with Sponsor Medical Monitor concurrence, that continuation with TTI-621 monotherapy would be reasonable and the patient meets guidelines for re-treatment with TTI-621 as described in [Section 9.2.2](#)
- Discontinuation of TTI-621 treatment

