**Table 17. Doxorubicin Dose Modifications**

Dose Level	Doxorubicin Dose
Dose Level 1	75 mg/m 
Dose Level -1	60 mg/m 
Dose Level -2	45 mg/m 

General guidelines for dose modifications in response to observed adverse events in presented in [Table 18](#). In consideration that doxorubicin is being used as a standard of care anti-cancer therapy in the enrollment patient population and based on Investigator and site experience with doxorubicin in the enrolled patient population, alternate dose modifications may be implemented after discussion with the Sponsor Medical Monitor.

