**Table 18. Doxorubicin Dose Modification Guidelines**

Worst Toxicity in Prior Cycle	Doxorubicin Dose for Next Cycle
Febrile neutropenia	
Thrombocytopenia with bleeding	Decrease doxorubicin one dose level
ANC Grade 4 for $\geq$ 7 days	
Cardiotoxicity, including any signs and symptoms of heart failure, greater than 10% decline in LVEF to below the LLN, greater than 20% decline in LVEF from any level, or LVEF $\leq$ 45%	Discontinue doxorubicin Consider initiation of dexrazoxane
Grade 3 organ toxicity	Decrease doxorubicin one dose level
Grade 4 organ toxicity	Discontinue doxorubicin
Hepatic impairment	
Serum bilirubin 1.5 – 3.0 mg/dL	50% dose reduction
Serum bilirubin 3.1 – 5.0 mg/dL	75% dose reduction
Serum bilirubin $>$ 5.0 mg/dL	Discontinue doxorubicin

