### 9.3.3.1. Cardiac Toxicity Related to Doxorubicin Administration

Cardiotoxicity is a recognized risk of doxorubicin that increases with higher cumulative drug exposure. Cardiac monitoring is conducted by a combination of monitoring of clinical parameters, ECG and echocardiogram (ECHO) / multigated acquisition (MUGA) scan. ECG changes, arrhythmias, tachycardia, and/or chest pain should be managed according to clinical practice based on the specific findings.

Patients will undergo baseline LVEF determination by ECHO or MUGA scan. This evaluation may be repeated at any time during the study if clinically indicated. A decrease in LVEF of  $\geq$  10% and below the lower limit of normal, or an absolute decrease of 20%, or if the absolute LVEF decreases to or below 40%, doxorubicin will be discontinued. Doxorubicin should also be discontinued if the patient develops Grade  $\geq$  3 left ventricular systolic dysfunction (symptomatic congestive heart failure).

If doxorubicin is discontinued for the above changes in LVEF despite optimal prophylaxis, the patient may be eligible to continue on study with TTI-621 monotherapy after discussion with the Sponsor Medical Monitor, provided that the patient has completed at least four cycles of doxorubicin therapy, is receiving clinical benefit and meets guidelines for re-treatment with TTI-621.

The diagnostic method used at baseline for cardiovascular assessments (for example ECHO or MUGA scans) should be the same method used throughout the study, unless there is clinical or instrumental evidence that further investigations are needed.

The use of dexrazoxane to reduce the incidence and severity of cardiomyopathy due to doxorubicin administration in patients who have received a cumulative doxorubicin dose of 300 mg/m^2 and who will continue to receive doxorubicin is recommended and will be implemented in this study. As described in [Section 5.2.1.1](#), prophylaxis with dexrazoxane for cardiotoxicity must begin no later than with initiation of Cycle 5 when cumulative doxorubicin will have reached 300 mg/m^2. Do not administer dexrazoxane as a cardioprotectant at the initiation of doxorubicin treatment unless that is the standard of care at a particular institution.

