**9.4. Management of Adverse Events not Attributable to a Specific Study Treatment**

Guidelines for managing adverse events when attribution to either TTI-621 or doxorubicin is not possible in the opinion of the Investigator are provided in [Table 21](#). Guidelines for management of treatment emergent thrombocytopenia are provided in Table 22 and Table 23 in [Section 9.5](#). Discussion with the Sponsor Medical Monitor is recommended to ensure homogeneity in adverse event management across all patients to the extent possible.

**Table 21. General Guidelines for Management of Adverse Events when Attribution is not Possible in the Opinion of the Investigator**

Note that guidelines for management of thrombocytopenia are provided in Table 22 and Table 23 in [Section 9.5](#)

Observation	Management Guidelines

Hematologic Toxicity
 
 
Grade <math>\geq</math> 3 neutropenia (ANC <math>< 1 \times 10^9/L</math>)
 
Grade <math>\geq</math> 3 anemia
 
Hemoglobin <math>< 8 \text{ g/dL}</math>
 
 
Non-Hematologic Toxicity
 
Grade <math>\geq</math> 3 events excluding:
 
 
Sub-optimally treated nausea, vomiting, diarrhea
 
Alopecia
 
Transient fatigue of a duration consistent with that associated with doxorubicin treatment (1-2 weeks)
 
Infusion-related reaction in the absence of described prophylaxis
 
Laboratory abnormalities that are asymptomatic and/or judged by the Investigator as not clinically significant for the patient
 
	
First Appearance
 
 
Delay study treatment until recovery to Grade <math>\leq 1</math> or baseline with ANC <math>> 1.0 \times 10^9/L</math>. If no recovery after a delay of <math>> 21</math> days, discontinue all study treatment.
 
Reduce doxorubicin and TTI-621 dose levels by one dose level.
 
 
First Re-Appearance
 
 
Delay study treatment until recovery to Grade <math>\leq 1</math> or baseline. If no recovery after a delay of <math>> 21</math> days, discontinue all study treatment.
 
Reduce doxorubicin and TTI-621 dose levels by one additional dose level.
 
 
Second Re-Appearance
 
 
Discontinue all study treatment.
 

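### Two stopping rules each carry two limits: doxorubicin stops at LVEF 45% or 40%, and a non-attributable hold ends treatment after 42 or 21 days from last dose

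*Protocol*

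**What the plan says.** **LVEF.** Section 9.3.3.1 discontinues doxorubicin for a fall of at least 10% that ends below the lower limit of normal (LLN), "or an absolute decrease of 20"%, "or if the absolute LVEF decreases to or below 40%, doxorubicin will be discontinued". Table 18 discontinues it for a fall of more than 10% to below the LLN, or "greater than 20% decline in LVEF from any level, or LVEF $\leq$ 45"%. The text introducing Table 18 adds that "alternate dose modifications may be implemented after discussion with the Sponsor Medical Monitor".

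**Hold limit.** For the same event, in nearly the same words, the synopsis withdraws a patient from all treatment when a drug would have "to be held for more than 42 days from the last administered dose and is not attributable to a particular agent of the combination regimen". Section 5.3 has "to be held for more than 21 days from the last administered dose and is not attributable to a particular agent of the combination regimen". Both carry the same exception, for meaningful clinical benefit with Sponsor Medical Monitor concurrence. For events of this kind Table 21 (Section 9.4) tells sites to delay until recovery and then reduce both drugs by one dose level: "If no recovery after a delay of > 21 days, discontinue all study treatment".

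**Schedule.** Section 5.2.2 gives doxorubicin "on Day 1 of each 21-day cycle for a maximum of six cycles (18 weeks"). Section 5.2.3 gives TTI-621 on Days 1 and 8 of those cycles. Table 24 schedules on-treatment LVEF before Cycles 5 and 8, and Section 9.3.3.1 allows a repeat at any time if clinically indicated.

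**The concern.** Each pair of limits decides whether a patient goes on receiving study drug. Two sites that both follow the protocol could act differently on the same patient: one stops a drug with cumulative cardiac toxicity and the other gives it, or one withdraws a patient from all treatment and the other waits for recovery. The permissions to depart from a default do not say which printed limit is the default. SAP Section 7.3 has the clinical team classify deviations as major or minor before database lock, and that needs a stated reference rule.

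**Working it through.** The plan gives no figure to reproduce, so the printed limits are set against each other.

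**1. LVEF**

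Inputs: entry LVEF above 50% (inclusion criterion 15) and the triggers above. Assumptions: whole-number baselines from 51 to 80, and an LLN of 50 or 55. The protocol gives neither the upper bound nor the LLN. With declines in percentage points:

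- Table 18 stops if (fall > 10 and value < LLN), or fall > 20, or value ≤ 45.
- Section 9.3.3.1 stops if (fall ≥ 10 and value < LLN), or fall ≥ 20, or value ≤ 40.

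All baseline and lower follow-up pairs were enumerated.

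- *Stopped by Table 18 only:* 10 pairs at either LLN: 51 to 42–45 (4), 52 to 43–45 (3), 53 to 44–45 (2), 54 to 45 (1). From a baseline of 55, a fall to 45 is already 10 points and below the LLN, so Section 9.3.3.1 stops it too.
- *Stopped by Section 9.3.3.1 only:* 15 pairs at either LLN, all exact-equality cases. At LLN 50 there are 4 falls of exactly 10 (56 to 46 through 59 to 49) and 11 of exactly 20 (70 to 50 through 80 to 60). At LLN 55 there are 9 (56 to 46 through 64 to 54) and 6 (75 to 55 through 80 to 60).
- *Merged rule*, (fall ≥ 10 and value < LLN), or fall ≥ 20, or value ≤ 45: it agrees with stopping when either passage stops on every pair, with 0 mismatches at both LLNs.

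Units matter. If the 10% is relative and the 20% stays in points, there are 0 Table-18-only pairs at LLN 46, 48, 50, 52 and 55. For example, 51 to 45 is a fall of 6/51 = 11.8%, which already meets the relative trigger when the LLN is above 45.

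The pair counts show where the rules part, not how many patients are affected, since no LVEF distribution is given. Of the scheduled checks, only the one before Cycle 5 falls while doxorubicin is still to be given. It governs at most 2 × 75 = 150 of 6 × 75 = 450 mg/m², one third. An unscheduled check could bring the conflict forward.

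**2. Hold limit, doxorubicin**

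Let d be the days past the planned dose. Days since the last dose are then 21 + d.

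| Source | Condition | Triggers at |
|---|---|---|
| Section 5.3 | 21 + d > 21 | d ≥ 1 |
| Synopsis | 21 + d > 42 | d ≥ 22 |
| Table 21, counted from due date | d > 21 | d ≥ 22 |
| Table 21, counted from last dose | 21 + d > 21 | d ≥ 1 |

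Section 5.3 and the synopsis therefore disagree for d = 1 to 21, which is 22 to 42 days from the last dose.

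**3. Hold limit, TTI-621**

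In Cycles 1 to 6 the dosing intervals alternate between 7 days (Day 1 to Day 8) and 14 days (Day 8 to the next Day 1). A delay of 21 days past the next planned dose is 7 + 21 = 28 or 14 + 21 = 35 days from the last dose, so no single from-last-dose figure corresponds to it.

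**The case against.** The best defence is that the protocol has ways to limit the damage. Alternate doxorubicin modifications may be agreed with the Medical Monitor, the hold criterion has its clinical-benefit exception, Section 9.4 recommends discussion with the Medical Monitor so that patients are managed alike, and Section 13.8 sets regular calls to review active patients. A site can satisfy both LVEF passages by stopping when either is met. Dexrazoxane is required from Cycle 5, so the two doses at stake are given under cardioprotection. All of that stands and reduces the likely harm. It does not say which limit is the default, and the protocol never states the either-passage reading. The 42-day limits in Sections 9.2.1 and 9.3.1 do not help, because they concern each agent separately.

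A reader might infer that Table 21 settles the hold conflict for the synopsis and flatly contradicts Section 5.3. The documents do not support that. Table 21 does not say where its delay starts: counted from the due date it equals the synopsis limit for doxorubicin, and counted from the last dose it equals Section 5.3. The due-date reading is the natural one, since an instruction to delay and then reduce the dose has little room to operate otherwise, but it is not stated.

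A reader might also infer that many patients fall between the two LVEF floors. Nothing supports that either: the gap is narrow, and under one reading of the units it is empty.

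**Conclusion.** Both inconsistencies are real and stand in the current text of protocol version 2.0. They should be corrected as patient-safety instructions.

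- **LVEF.** The floors differ by 5 points, the companion triggers differ at the boundary, and the units are not stated consistently. With declines in points, the 45/40 gap bites only for baselines 51 to 54. It disappears if the 10% is relative and the LLN exceeds the observed value. Section 9.3.3.1 is the stricter passage only for falls of exactly 10 or 20 points.
- **Hold.** The conflict is firm between Section 5.3 and the synopsis, for doxorubicin delays of 1 to 21 days and subject to the clinical-benefit exception. Section 5.3 read literally allows no doxorubicin delay, which is hard to square with Table 21.

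It would be tempting to carry this through to the trial's conclusions. That does not follow: no sample size, response criterion, Simon boundary or planned efficacy analysis depends on either limit. Deviations can still be classified by accepting either printed version, provided that this is stated.

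**What to change.** 1. **LVEF.** Put one rule in Table 18 and Section 9.3.3.1, in absolute percentage points, that stops doxorubicin whenever either present passage would: LVEF ≤ 45%; a fall of ≥ 10 points to below the LLN; or a fall of ≥ 20 points. The clinical team may justify other values, but both places must agree.
2. **Hold.** In Section 5.3 replace 21 with 42 days from last dose, as in the synopsis. In Table 21 state that delay is counted from the planned Day 1 of the next combination cycle, so that more than 21 days late is more than 42 days from the last doxorubicin dose. In the combination period, use this cycle-start clock for both drugs and set no separate TTI-621 limit from its own last dose. Say that a Day 8 dose omitted under Table 22 is not a delay.
3. **If dosing is finished.** SAP Section 4.3.2 reports the Cohort C patients as already enrolled, and doxorubicin lasts at most 18 weeks. In that case, state which version counts as compliant before deviations are finalised, and identify patients in either conflict band from listings already planned (SAP Section 9.1 for planned and actual dosing dates and reasons for cycle delay; Section 6.8 for all recorded data).

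The cost is a clarification letter or an amendment of a few lines, or only the compliance statement and a check of existing listings. There is no statistical cost.

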### **9.3.3.2. Secondary Malignancies Related to Doxorubicin Administration**

The risk of developing secondary acute myelogenous leukemia is increased following treatment with doxorubicin. Cumulative incidences ranged from 0.2% at five years to 1.5% at 10 years in two separate trials involving the adjuvant treatment of women with breast cancer. These leukemias generally occur within 1 to 3 years of treatment.

### **9.3.3.3. Extravasation and Tissue Necrosis Related to Doxorubicin Administration**

Extravasation of doxorubicin can result in severe local tissue injury manifesting as blistering, ulceration, and necrosis requiring wide excision of the affected area and skin grafting. When given via a peripheral venous line, infuse doxorubicin over 10 minutes or less to minimize the risk of thrombosis or perivenous extravasation. If signs or symptoms of extravasation occur, immediately terminate the injection or infusion. Extravasation may be present in patients who do not experience a stinging or burning sensation or when blood return is present on aspiration of the infusion needle. If extravasation is suspected, apply ice to the site intermittently for 15 minutes, 4 times a day for 3 days. If appropriate, administer dexrazoxane at the site of extravasation as soon as possible and within the first 6 hours after extravasation.

### **9.3.3.4. Hematologic Toxicity Related to Doxorubicin Administration**

ASCO guidelines for use of WBC growth factors provide that 'prophylactic use of WBC growth factors for prevention of febrile neutropenia is warranted when the risk of febrile neutropenia is approximately 20% or higher and no other equally effective and safe regimen that does not require CSFs is available. Primary prophylaxis is recommended for the prevention of febrile neutropenia in patients who are at high risk on the basis of age, medical history, disease characteristics, and myelotoxicity of the chemotherapy regimen. The NCCN guidelines for hematopoietic growth factors classify soft tissue sarcoma treated with doxorubicin as an example of disease setting and chemotherapy regimen with a high risk for febrile neutropenia (>20%) and recommends G-CSF prophylaxis for patients with high risk (>20%) of febrile neutropenia.

Thus, all patients receiving TTI-621 in combination with doxorubicin should receive prophylaxis with G-CSFs for prevention of febrile neutropenia associated with doxorubicin. Suggested prophylaxis is pegfilgrastim and discussion with the Sponsor Medical Monitor regarding the specific agent is encouraged.

Doxorubicin will not be administered in Cycles 2 – 6 if the patient's ANC is  $< 1 \times 10^9$  cells/L or if the platelet count is  $< 75 \times 10^9$  cells/L. When necessary, the next treatment cycle should be delayed until the ANC is

$\geq 1 \times 10^9$  cells/L and the platelet count is  $\geq 75 \times 10^9$  cells/L and non-hematologic toxicities have resolved. For patients who experience Grade  $\geq 3$  neutropenic fever or infection or Grade 4 neutropenia without fever lasting more than 1 week, doxorubicin should be reduced to 75% of the starting dose (to approximately 60 mg/m^2). If a patient experiences a second incidence of neutropenic fever or infection or has another episode of Grade 4 neutropenia lasting  $> 1$  week, then a second dose reduction to 45 mg/m^2 should be implemented. Doxorubicin dose reductions for neutropenia are described in [Table 19](#).

Therapeutic and prophylactic use of G-CSFs will be allowed per current ASCO and NCCN guidelines. For patients with Grade 4 ANC without fever/infection lasting less than one week, re-treatment will be allowed at the Investigator's discretion with the full dose of doxorubicin (75 mg/m^2) with recommended use of G-CSFs per current ASCO guidelines.

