**Table 19. General Guidelines for Doxorubicin Dose Reduction due to Neutropenia**

Observation	Management Guidelines
ANC < 1 x 10  cells/L	
 
Doxorubicin not administered; treatment cycle delayed
 

At Re-Treatment: 
 
Grade 3 neutropenic fever/infection has occurred
 
If Grade 4 neutropenia lasting > 1 week has occurred
 
Grade 4 ANC without fever/infection
 
	
 
Reduce doxorubicin dose to 60 mg/m^2
 
Reduce doxorubicin dose to 60 mg/m^2
 
Re-treatment with doxorubicin at full dose at Investigator's discretion with prophylactic G-CSF
 

Second Incidence of either Grade $\geq$ 3 neutropenic fever/infection or Grade 4 neutropenia lasting > 1 week	
 
Reduce doxorubicin dose to 45 mg/m^2
 

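### Protocol Section 9.3.3.4 equates 75% of the doxorubicin starting dose with about 60 mg/m², but 75% of 75 mg/m² is 56.25 mg/m² and 60 mg/m² is 80%

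*Protocol*

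**What the plan says.** Protocol Section 5.2.2 sets the doxorubicin dose: "at a dose of 75 mg/m 2 on Day 1 of each 21-day cycle". Section 9.3.3.4 names the same 75 mg/m² as the full dose when it covers Grade 4 neutropenia without fever lasting less than a week.

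Section 9.3.3.4 also covers patients with Grade 3 or higher neutropenic fever or infection, or with Grade 4 neutropenia without fever lasting more than one week. For them it says "doxorubicin should be reduced to 75% of the starting dose", and a parenthesis in the same sentence gives the result as approximately 60 mg/m². On a second such episode, "a second dose reduction to 45 mg/m 2 should be implemented". The paragraph then refers the reader to Table 19.

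Three tables bear on the same step:

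- **Table 17** lists the dose levels as 75, 60 and 45 mg/m². Section 9.3.3 says this scheme is the one to be used for adverse-event modifications.
- **Table 18** answers febrile neutropenia, or Grade 4 ANC for seven days or more, with a decrease of one dose level. Through Table 17 that is 60 mg/m².
- **Table 19** says "Reduce doxorubicin dose to 60 mg/m 2" for both neutropenia triggers, with no percentage and no qualifier.

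**The concern.** The percentage and the absolute dose appear in one sentence as two descriptions of the same reduction, and they give different doses. The percentage is not obviously decorative. Section 5.2.2 requires the doxorubicin dose to be calculated at the start of each cycle, and Table 18 gives its hepatic-impairment reductions only as percentages, so calculating from a percentage is a normal operation in this part of the protocol.

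The rule may well be used. Section 9.3.3.4 itself cites a guideline that places doxorubicin-treated soft tissue sarcoma above 20% risk of febrile neutropenia, which is the reason for G-CSF prophylaxis. What is at stake is consistent dosing of the first reduction across sites.

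**Working it through.** **Inputs**

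- Starting dose: 75 mg/m² (Section 5.2.2; Table 17, Dose Level 1; Section 9.3.3.4).
- First reduction in the text: 75% of the starting dose, glossed as approximately 60 mg/m² (Section 9.3.3.4).
- First reduction in the tables: 60 mg/m² (Table 17, Dose Level -1; Table 19).
- Second reduction: 45 mg/m² (Section 9.3.3.4; Tables 17 and 19).
- Doxorubicin is given for at most six cycles, so at most five cycles (2 to 6) can be reduced.

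**Attempt to reproduce the stated figure**

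- 0.75 × 75 = 56.25 mg/m², not 60.
- 60 / 75 = 0.80, so the absolute figure is 80% of the starting dose.

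**Other readings tried**

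- Rounding 56.25 to the nearest 5 gives 55. Rounding to the nearest 10 gives 60, but the protocol states no rounding rule for doxorubicin. The rounding allowance in Section 8.3.1 concerns body weight for TTI-621.
- A reduction by 75% leaves 0.25 × 75 = 18.75 mg/m².
- The starting dose for which 75% equals 60 is 60 / 0.75 = 80 mg/m², which the protocol does not use.
- 75% of the previous level fits the second step (45 / 60 = 0.75) but not the first, and the text says the percentage is of the starting dose. On that basis 45 mg/m² is 45 / 75 = 60%.

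Only the unstated rounding to the nearest 10 connects the two figures.

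**Size of the discrepancy**

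- Per reduced cycle: 60 − 56.25 = 3.75 mg/m². This is 3.75 / 60 = 6.25% of the tabulated dose, or 3.75 / 56.25 = 6.7% of the dose calculated from the percentage.
- Upper bound over five reduced cycles: 5 × 3.75 = 18.75 mg/m².
- Cumulative dose in that extreme case: 75 + 5 × 60 = 375 mg/m² against 75 + 5 × 56.25 = 356.25 mg/m². The difference is 18.75 / 375 = 5%.

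**The case against.** The strongest reply is that the operative dose is already fixed. The sentence carries its own mg/m² figure, the paragraph sends the reader to Table 19, and Section 9.3.3 makes the Table 17 scheme the one to use. Tables 17, 18 and 19 all arrive at 60 mg/m². To give 56.25 mg/m², a site would have to set all of that aside. The word approximately also signals that the percentage is loose. Table 19 is headed as general guidelines, and the text under Table 17 describes Table 18 in the same way and allows alternate modifications after discussion with the Sponsor Medical Monitor.

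Much of this stands, and it limits the consequence. It does not make the sentence consistent: approximately is not a rounding rule, the tables carry no such qualifier, and nothing tells a reader of Section 9.3.3.4 to disregard the percentage.

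Three stronger readings are tempting, and the documents do not support them.

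- **A reader might infer that sites would deliver different doses.** The text supports only that they could, because the absolute figure sits beside the percentage and in the tables.
- **A reader might infer that the SAP exposure analysis is compromised.** SAP Section 9.1 defines cumulative dose as the sum of doses actually received and reports dose reductions as numbers of participants. Neither derivation uses the 75% figure. Actual variation in dosing would be recorded as it occurred, not miscalculated.
- **A reader might infer that agreement among the tables settles which figure was meant.** It shows that the percentage is the outlier. It does not establish intent, which is for the sponsor to state.

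**Conclusion.** The point holds as an internal inconsistency: the percentage and the absolute dose in Section 9.3.3.4 cannot both be right for a 75 mg/m² starting dose, and the percentage also disagrees with Tables 17, 18 and 19.

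Its practical size is small. The possible difference is 3.75 mg/m² per reduced cycle. The total of 18.75 mg/m² is a ceiling. It assumes a qualifying event in Cycle 1, all five remaining cycles given at the first reduced level, no second event that moves the dose to 45 mg/m², and a site that uses the percentage throughout.

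The Simon two-stage sample size, power, Type I error and decision rule do not depend on this figure. The DLT-evaluable definition rests on the full Cycle 1 dose, which comes before any such reduction. The point is minor, but worth correcting because the figure is part of a dosing instruction.

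**What to change.** Reconcile the percentage and the mg/m² figure in Section 9.3.3.4 with each other and with Tables 17, 18 and 19. The sponsor states which value is intended; this review takes no position on the dose. One way to keep the statements aligned is to define the reduction once, by reference to the Table 17 dose levels, and not restate it as a percentage.

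The cost is one corrected figure or a short clarification to sites, with no change to the SAP. If patients have already had a first reduction under this section, the study drug administration listings planned in SAP Section 9.1 can be used to check which reading was applied.
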